July 18, 2014

Title: Pilot study: randomized, placebo-controlled comparator trial of IV vs oral iron treatment of RLS with Iron deficiency anemia. (IVOR-IDA)

Principal Investigator: [name].

INTRODUCTION

Summary: The restless legs syndrome (RLS), also known as Willis-Ekbom Disease, occurs in 40-50% of patients with iron deficiency (ID) or its end stage, iron deficiency anemia (IDA) (Achebe, AJH, 2023). Treatment correcting the ID is expected to also be effective for reducing or eliminating the RLS with IDA. Two accepted treatments for IDA, oral ferrous sulfate and ferumoxytol were compared for efficacy and speed of response for treatment of RLS occurring with IDA (RLS-IDA). The original plan for this study was the accrual of 70 RLS-IDA patients to be randomly assigned 35 each to oral or IV iron using double-blind, double-dummy procedures. The primary outcome was determined at 6 weeks of treatment. Following initial evaluation, due to complications of performing a clinical trial during the pandemic and the death of the principal investigator, it was determined that the patient and clinical global impression scores, primary outcomes for the trial, were missing in 30 patients. As a result, in order to maintain the prespecified statistical analysis, an additional 30 patients were accrued.

Background: Low iron status is associated with RLS. RLS has been documented to have significant decreased iron concentrations in the substantia nigra (Allen, Neurology, 2001) and other areas (Rizzo, Movement Disorders, 2013). These associations have been documented into studies using both magnetic resonance imaging (Allen, Rizzo, [name] Sleep Med 2006) and ultrasound (Schmidauer, Ann Neuro 2005). Peripheral iron status also relates to RLS severity (Sun, Sleep 1998) and both oral and IV iron treatments significantly reduce RLS symptoms compared with placebo (Allen, Sleep Med 2011 and Wang, Sleep Med 2009).

RLS occurs commonly with IDA. In the single institution in which the study was performed the prevalence of clinically significant RLS was approximately 45% (Achebe, AJH). This is approximately seventeen times the prevalence of any RLS in the general population. Standard treatments for IDA also treat RLS without IDA. Both oral and IV iron are considered standard treatments for IDA (Schrier, UTD 2013). These same treatments also reduce RLS symptoms. Oral iron as ferrous sulfate containing 60 mg of elemental iron per tablet, taken twice daily produced significant reduction of RLS symptoms in a blinded placebo-controlled study (Wang, Sleep Med). IV iron administered as ferric carboxymaltose in two doses of 750 mg spaced five days apart, also reduced RLS symptoms significantly more than placebo (Allen, Sleep Med).

Rationale for study: It is assumed the treatments which reverse IDA will also reduce the RLS symptoms occurring with IDA. This is supported by the benefit observed in RLS patients without IDA. However, this benefit has never been demonstrated in a prospective controlled trial, especially in a blinded study. The iron stores, however, are less in those with IDA than in the general population and

therefore IDA-RLS may require more aggressive treatment than is used for RLS without IDA and possibly even more aggressive therapy than is usually administered for IDA. In particular, despite the recovery of anemia after six weeks of oral iron therapy, the actual iron stores remain low. In contrast the IV iron treatment with 1000 mg of IV iron corrects the anemia and provides a better increase in iron parameters over a 6-week period (Schrier UTD, 2013). Accordingly, if the IDA-RLS results more from the low iron than the anemia, it may benefit significantly more from IV than oral iron [BUT IT DIDN'T—DAMNIT!].

Our major problem in testing the treatment benefits for IDA-RLS for either oral or IV iron was not knowing the actual effect size of either treatment. We had as an initial estimates the effect sizes from clinical experience with oral and IV iron therapy for IDA-RLS. Thus, we set the sample size to give adequate power to differentiate IV from oral iron assuming these estimates, without knowing if the estimates were accurate. The decision not to do a placebo control is based on the assumption that the treatment effect size can be adequately determined without a placebo. The decision to use a blinded comparator trial was based on the assumption that we would see differences between the treatments.

METHODS

The study was a randomized, comparative, double-blind study to evaluate effect size and time course of treatment response for RLS-IAD over six weeks. Two medications and two placebos were used with equal random assignment to both groups:

1. *FCM group:* Oral vitamin C, 500 mg tablets taken twice a day (placebo pill) and Ferumoxytol intravenous (IV) 1020 mg in two divided doses over 15 minutes 2-7 days apart
2. *FeSO4 group:* Ferrous sulfate 325 mg (oral) tabs morning and evening and IV saline given over 15 minutes 2-7 days apart (placebo infusion)

IV ferumoxytol, 1020 mg was be offered to those not significantly responding (CGI-I scores less than much or very much improved) at 6 weeks after oral iron and still meeting all the requirements for entry to study.

All patients who presented to a single outpatient Hematology clinic for treatment for their iron deficiency anemia (IDA), completed the Cambridge-Hopkins diagnostic questionnaire (CDQ) as part of their routine clinical evaluation, which was not limited to its use in this study. Those identified by the questionnaire as having RLS were checked for meeting the other inclusion criteria. The research coordinator reviewed the responses to the questionnaire, their clinical history and recent blood values to ensure inclusion criteria were met. If all criteria were met, the research coordinator consented the

patient for enrollment in the study. After consenting, a protocol number was assigned and appropriate blood samples obtained. Diagnosis of RLS was then confirmed by Hopkins-Hening Telephone Diagnostic Interview (HTDI) conducted by [name] or [name].

A xcel-generated randomization table was used to randomly assign subjects to one of two treatment conditions. Blinding was done by a separate and independent "treatment nurse" who used the randomize table, made the assignments on the day of treat and then completed the appropriate treatment. The randomization was in 7 blocks of 10 with equal treatments in each block. The research coordinator did not know the treatment administered and was not present during treatment and did not have access to files indicating, which treatment was administered. During IV infusions, the patients wore sleep masks that fully covered their eyes to ensure they did not notice any color differences between the iron and placebo administration. All investigators and the Analysts were blind to the assignment until completion of the analysis.

Two IV treatments spaced 2-7 days apart were administered. These were either ferumoxytol or placebo. At the time of the first infusion, an opaque bottle containing either vitamin C or ferrous sulfate was given to the subject. The patient was instructed to take each of the pills twice a day for the next six weeks. Enough pills to last 7 seven weeks were given to allow for ongoing treatment for the follow-up appointment at six weeks after the first IV infusion.

For IV iron treatment, the commercially available ferumoxytol was used. Ferumoxytol is marketed as an iron replacement formulation indicated for the treatment of iron deficiency anemia and is FDA approved for this indication. Ferumoxytol (30 mg/mL) is available for IV injection in single use vials containing 510 mg of elemental iron in 17 mL. Ferumoxytol is stored at controlled room temperature (20-25° C). Pre-treatment medications were not administered. 510 mg of ferumoxytol was diluted in 100 ml normal saline and administered with an infusion pump over a 15-minute period. Vital signs were measured and recorded immediately prior to drug administration and were observed for 60 minutes following completion of the infusion with observation for signs or symptoms of adverse events. For the placebo (normal saline) administration was exactly the same procedure as the IV iron formulation.

For oral iron, ferrous sulfate 325 mg tablets containing 65 mg of elemental iron were used. The pills were taken twice daily on an empty stomach. If significant gastrointestinal perturbation occurred the medication could be taken with food. The oral placebo was standard vitamin C 250 mg tablets given in the same bottle as oral iron.

Following the first IV infusion, telephone evaluations were performed at 7, 14 and 28 days. At four weeks after the first of the pair of IV treatment were completed, blood tests were performed to include hemoglobin concentration and iron parameters (serum iron, total iron binding capacity, serum ferritin, percent transferrin saturation). A six weeks after the first of the pair of IV treatment were completed, another clinic visit was scheduled so a CGI form could be completed by involved medical personnel. At 6 weeks, non-responders were given the option of receiving ferumoxytol as an open-label infusion. At the 6-week clinic visit, repeat blood tests (see above), adverse event reporting and clinical evaluation of the RLS was performed.

Inclusion criteria were as follows:

1. Aged \geq 18 years
2. Diagnosis of RLS based on CHDQ and confirmed by HTDI
3. International RLS Study Group Severity Scale (IRLS) score > 15 .
4. Iron deficiency anemia defined as ID either ferritin < 20 mcg/l, TSAT $< 19\%$, anemia Hb < 13 g/dL for both males and females.
5. Willingness to use contraceptive to avoid pregnancy: Women have to be surgically sterile, post menopausal or use one of the following contraceptives during the whole study period and after the study has ended for at least 5 times plasma biological half-life of the investigational medicinal product: intrauterine devices or hormonal contraceptives (contraceptive pills, implants, transdermal patches, hormonal vaginal devices, or injections with prolonged release).
6. Willingness to participate and signing the informed consent form

Exclusion criteria were as follows:

1. Iron overload or disturbances in utilization of iron (e.g. haemochromatosis and hemosiderosis)
2. Decompensated liver cirrhosis or active hepatitis (ALAT > 3 times upper limit of normal)
3. Serum ferritin > 500 ng/mL or transferrin saturation $> 40\%$
4. Active acute or chronic infections (assessed by clinical judgment that may be indicated by white blood cells (WBC) and C-reactive protein (CRP) when these are available)
5. Rheumatoid arthritis with symptoms or signs of active inflammation
6. Pregnant and nursing women
7. History of multiple allergies
8. Known hypersensitivity to parenteral or oral iron or any excipients in the drug products
9. Previous IV iron treatment for RLS
10. Other iron treatment or blood transfusion within 4 weeks prior to the screening or treatment visit
11. Planned elective surgery during the study
12. Current (past 4 weeks) use of drugs that treat RLS, e.g. opioids, alpha-2-delta anti-depressants, dopaminergic agents (dopamine promoters, dopamine antagonists/blockers)

Any other medical condition that, in the opinion of Investigator, may cause the subject to be unsuitable for the completion of the study or place the subject at potential risk from being in the study, e.g. a malignancy, uncontrolled hypertension, unstable ischemic heart disease, or uncontrolled diabetes mellitus.

The following endpoint were used for the study:

1. At evaluation in the clinic at about 6 weeks after the first IV iron treatment.
2. Termination of participation because of significant adverse effect from the IV infusion in the hour observed after the infusion.
3. Significant adverse event after starting the iron treatment and before the 6 week follow-up evaluation that was judged to require ending the study.
4. Subject decision not to continue in the study after the treatment and before the final evaluation.
5. Physician's decision that it would be harmful to the patient to continue in the study.
6. Patient is non-compliant with study requirements and was judged the non-compliance was enough to significantly alter evaluation of the treatment. (Note that stopping the oral medication because of intolerance to the treatment is not considered non-compliance, but rather an outcome for the study). Patients discontinuing oral medication for adverse effects may qualify for repeat IV treatment.

Subjects could terminate the study at any time for could be terminated from the study for non-compliance or if continuation in the study was judged by the PI ([name]) to be harmful. Reasons for termination were recorded. 21 patients were terminated or lost to follow-up. Some of these terminations may have been due to hiatuses in the study caused by the untimely death of the principal investigator ([name]) and the untimely occurrence of the COVID pandemic, interfering with patient visits. A list of those terminated or lost to follow-up are reported in Table _____. As a result, an additional 30 patients were accrued above the planned prespecified number, to achieve appropriate statistical power.

There were two co-primary outcome measures: Clinician Global Inventory-Improvement (CGI-I) assessment at week 6 and the change-in-baseline at 6 weeks in International RLS Study Group Severity Scale (IRLS) score. The Patient Global Inventory-Severity (PGI-S) was a secondary outcome measure (PGI-S). The IRLS and PGI-S were obtained at the clinic visits and at each telephone evaluation, while the CGI-i was only obtained at the Week-6 study endpoint.

Statistical analysis

Baseline and follow up laboratory values were described overall and within each study group. Means and standard deviations and medians and ranges were produced for continuous variables, and frequency counts and percentages were generated for describing variables that were dichotomous or

polytomous in nature. Changes in laboratory values from baseline to follow up were calculated and the mean change in values was compared using t-tests.

Results

Baseline lab values of all subjects and by Group are found in Table 1. There was a significant difference between baseline ferritin and TSAT values. Group A had a higher baseline ferritin and TSAT values than Group B.

Change in hemoglobin and iron parameters for all subjects and by group are shown in Table 3. The mean change in hemoglobin from baseline to follow up was 1.2 (SD 1.3) for Group A and 6.0 (17.2) for Group B. The mean change in Ferritin from baseline to follow up was 200.3 and 23.3 for Group A and Group B, respectively. The mean change in TSAT from baseline to follow up was 16.5 and 12.2 for Group A and Group B, respectively. The mean change in MCV from baseline to follow up was 24.2 and -17.6 for Group A and Group B, respectively. There was a significant difference between follow up ferritin and TSAT values. Group A had a higher follow up ferritin values ($p=0. <0.0001$) and higher TSAT ($p=0.007$) values compared to Group B.

Table 4 shows the changes in patient severity scores from baseline to follow up, and the follow up patient and clinical global impression scores for all subjects and by group. No significant differences between the 2 groups in terms of change in (1) patient severity score from baseline to follow up, (2) follow up patient global impression score, or (3) clinical global impression score were observed.

Table 5 shows the change in FSS from baseline to follow up. There were no significant differences between the 2 groups in terms of change in FSS.

Table 6 shows the change in IRLS score from baseline to follow up for all subjects and by group. Group B had a greater reduction in IRLS score from baseline to follow up compared to Group A

NOT SURE IF/HOW YOU WANT TO PRESENT THE ADVERSE REACTION DATA

Commented [VS1]: These are results from my original analysis. I still need to double check the results. However, before doing so, I want to confirm that there are no new data to analyze.

Commented [VS2]: Will define "Group A" and "Group B" once I know which group is which

TABLES**Table 1. Baseline hemoglobin and iron parameters for all subjects and by group.**

	Total	Group A	Group B	P-value¹
Hemoglobin	N=93	N=47	N=46	0.14
Mean (SD)	11.1 (1.5)	11.3 (1.3)	10.8 (1.6)	
Median (IQR)	11.6 (10.2, 12.2)	11.7 (10.8, 12.3)	11.6 (9.7, 12.1)	
Min, Max	7.0, 13.1	7.2, 13.1	7.0, 13.0	
Ferritin	N=91	N=45	N=46	0.017
Mean (SD)	17.9 (16.7)	22.6 (19.6)	13.5 (12.1)	
Median (IQR)	11.0 (7, 24)	19 (7, 29)	10.0 (7-15)	
Min-Max	3, 102	4, 102	3.0, 59.0	
TSAT	N=92	N=46	N=46	0.025
Mean (SD)	10.4 (6.2)	11.4 (5.9)	9.5 (6.5)	
Median (IQR)	9.0 (6, 13)	10.0 (8, 15)	8.5 (6.0-11.0)	
Min-Max	2, 36	2, 36	2, 32	
MCV	N=93	N=47	N=46	0.233
Mean (SD)	88.7 (77.3)	82.2 (7.8)	95.4 (110.4)	
Median (IQR)	83 (75.5, 87.0)	83.9 (77.9, 86.3)	81.5 (71.6-87.0)	
Min-Max	56.5, 825.0	58.7, 100.0	56.5, 825.0	

¹ P value comparing Group A vs. Group B using Kruskal-Wallis Test.

Table 2. Follow-up hemoglobin and iron parameters for all subjects and by group.

	Total	Group A	Group B	P-value¹
Hemoglobin	n=70	N=36	N=33	.833
Mean (SD)	14.4 (11.8)	12.5 (1.0)	16.6 (17.0)	
Median (IQR)	12.4 (11.7, 13.3)	12.6 (11.9, 13.2)	12.3 (11.7, 13.4)	
Min-Max	9.7, 105.0	10.4, 14.3	9.7, 105.0	
Ferritin	n=70	N=36	N=33	<0.0001
Mean (SD)	132.8 (136.7)	223.4 (136.6)	37.1 (29.5)	
Median (IQR)	66.5 (27.0, 214.0)	209.5 (127.5, 308.5)	33.0 (21.0-40.0)	
Min-Max	7.0, 620.0	11.0, 620.0	7.0, 159.0	
TSAT	n=70	N=36	N=33	0.026
Mean (SD)	24.4 (13.3)	27.7 (10.0)	21.4 (15.5)	
Median (IQR)	24.0 (14.0, 31.0)	28.0 (20.5, 32.0)	16.0 (12.0-28.0)	
Min-Max	7.0, 89.0	13.0, 59.0	7.0, 89.0	
MCV	n=70	N=36	N=33	0.21
Mean (SD)	95.1 (93.7)	106.4 (130.2)	83.3 (10.6)	
Median (IQR)	86.0 (82.0-88.6)	86.8 (82.7, 88.8)	85.1 (80.0-88.1)	
Min-Max	36.8, 864.0	36.8, 864.0	38.7, 101.0	

¹ P value comparing Group A vs. Group B using Kruskal-Wallis Test.

Table 3. Change in hemoglobin and iron parameters from baseline to follow up for all subjects and by group.

	Total	Group A	Group B	P-value¹
Hemoglobin	N=70	N=36	N=33	0.17
Mean (SD)	3.5 (12.0)	1.2 (1.3)	6.0 (17.2)	
Median (IQR)	1.4 (0.2-2.3)	1.4 (0.2, 1.8)	1.7 (0.3, 3.3)	
Min-Max	-0.9, 95.6	-0.9, 5.0	-0.9, 95.6	
Ferritin	N=67	N=34	N=33	<0.0001
Mean (SD)	113.1 (130.4)	200.3 (133.0)	23.3 (21.2)	
Median (IQR)	35.0 (18, 579)	190.0 (103.0, 290.0)	20.0 (9.0, 27.0)	
Min-Max	-7, 579	-1.0, 579.0	-7.0, 102.0	
TSAT	N=68	N=35	N=33	0.007
Mean (SD)	14.4 (12.6)	16.5 (7.5)	12.2 (16.3)	
Median (IQR)	13.5 (6.5, 19.4)	16.0 (11.0, 20.0)	7.0 (3.0, 18.0)	
Min-Max	-17.0, 82.0	-5.0, 37.7	-17.0, 82.0	
MCV	N=70	N=36	N=33	0.49
Mean (SD)	4.2 (129.9)	24.2 (130.9)	-17.6 (129.5)	
Median (IQR)	3.2 (-0.2, 8.2)	3.3 (-0.4, 7.6)	3.1 (1.2, 9.5)	
Min-Max	-736.9, 784.4	-58.4, 784.4	-736.9, 21.1	

¹ P value comparing Group A vs. Group B using Kruskal-Wallis Test.

Table 4. Change in patient severity scores from baseline to follow up, and follow up patient and clinical global impression scores for all subjects and by group.

	Total	Group A	Group B	P-value¹
Change in patient severity score²	N=57	N=30	N=27	0.24
Mean (SD)	-1.9 (1.8)	-1.7 (1.8)	-2.1 (1.9)	
Median (IQR)	-2.0 (-3.0, -1.0)	-2.0 (-3.0, -1.0)	-3.0 (-4.0, -1.0)	
Min-Max	-5.0, 2.0	-5.0, 2.0	-5.0, 2.0	

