The percentage responding will be evaluated for each drug condition to determine overall effect size at 6 weeks after treatment. This will be calculated for the IRLS scale and the PGI as change from baseline and for the CGI with response determined as much or very much improved (scores of 1 or 2). All scores greater than 2 on the CGI are considered to indicate no significant response. The onset of treatment will be described as the percentage showing much or very much improvement at each of the evaluations and by the change in IRLS score from baseline at each evaluation. The duration of treatment over the 12 month follow up will be described as the percentage of responders and the IRLS change from baseline at each time point for both oral and IV iron. The oral iron treatment will be stopped for all subjects at the 6-week time point.

The outcomes for the oral versus IV treatments at 6 weeks will be compared using a standard unpaired unequal variance t-test for the change in IRLS scores from baseline. The number of responders compared to no-responders will be compared using the Fisher Exact test.

Sample Size

Uncontrolled experience observing IDA patients with RLS indicated that about 80% responded to IV iron (about 1000mg dose) and 50% responded to standard oral iron treatment over 6 to 12 weeks. These percentage outcomes require a sample size of 70 (35 with each treatment) to provide a power of >80% with alpha = 0.05 to test for differences between these treatments. This was considered a reasonable sample to ascertain the effect size of the two treatments and to provide enough positive outcomes to evaluate time course for improvement with treatment and persistence of the treatment effect.

Breaking the blind

The randomization is in cohort blocks of 10, 5 with each treatment. The blind for the form of initial treatment will be broken for every cohort of 10 treated patients after all members of a cohort have completed the study. The blind may also be broken for specific subjects if the treatment information is needed for medical care of the patient.

Concomitant Medication

Permitted Medications

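### The SAP is dated 18 July 2014 but postdates group-level results, and it raises IRLS change from second-step test to co-primary without marking the departure

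*SAP*

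**What the plan says.** **SAP, header and Introduction (Summary).** The header date is 18 July 2014, the same as the protocol's. The Summary cites a 2023 publication. It explains that, "due to complications of performing a clinical trial during the pandemic and the death of the principal investigator", the patient and clinical global impression scores, "primary outcomes for the trial, were missing in 30 patients", and that "in order to maintain the prespecified statistical analysis, an additional 30 patients were accrued".

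**SAP, Rationale for study and Results.** After the sentence suggesting that IV iron may do better than oral, the text adds "BUT IT DIDN'T—DAMNIT". Results by group follow, with the margin comment "These are results from my original analysis. I still need to double check the results" and the statement that "Group B had a greater reduction in IRLS score from baseline to follow up compared to Group A".

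**SAP, Methods and tables.** The outcome paragraph before Statistical analysis names two co-primary outcomes, CGI-I at week 6 and IRLS change at week 6, with no order and no division of alpha. The Statistical analysis section covers only descriptive summaries and t-tests of laboratory changes. Kruskal-Wallis appears only in the table footnotes. A note under Table 4 has the most recent value used when the week-6 value is missing.

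**Protocol, same date.** Study Design makes CGI-2 at 6 weeks the primary outcome. The tertiary/exploratory objectives set a hierarchy for the between-arm comparison: percentage of CGI-2 responders first, IRLS change second. Statistical Analyses assigns an unequal-variance t-test to IRLS change and, for response, states: "The number of responders compared to no-responders will be compared using the Fisher Exact test".

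**The concern.** A SAP with a 2014 date is normally taken as fixed before the data, so a reader would take what it contains as planned. Here three choices have no source in the protocol: the co-primary rank of IRLS change, the Kruskal-Wallis tests for CGI and IRLS, and the most-recent-value rule. The SAP does not flag any of them as a change.

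At stake is the one efficacy comparison below 0.05. If IRLS change is taken as a planned co-primary, p=0.047 is a positive primary finding. If it is the second step of a hierarchy, it depends on the first step. Direction adds weight. Group B improved more on IRLS, and the mean ferritin change (200.3 in A, 23.3 in B) suggests that B is the oral-iron arm, although the SAP does not identify the groups. The misdated document could therefore support a claim that a planned primary outcome favoured oral iron.

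**Working it through.** **1. Dating.** The header says July 2014. The text cites a 2023 publication, describes the pandemic and the added patients, and contains group-level tables. The text as it stands therefore postdates group-level results.

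**2. Protocol against SAP.**

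| Item | Protocol | SAP |
|---|---|---|
| Primary outcome | CGI-2 at 6 weeks | CGI-I and IRLS change, co-primary |
| Order of between-arm tests | CGI-2 responders, then IRLS change | None; no alpha split |
| CGI test | Fisher exact on responders (score 1 or 2) | Kruskal-Wallis on scores, p=.80 (Table 4) |
| IRLS test | Unequal-variance t-test | Kruskal-Wallis, p=0.047 (Table 6) |
| Missing week-6 value | No rule | Most recent value |

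The SAP is not consistent on rank either. Its Summary calls the global impression scores the primary outcomes, while its Methods put IRLS change beside CGI-I.

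**3. Does the change of test matter for IRLS?** The Kruskal-Wallis p=0.047 cannot be reproduced without patient data. The protocol's Welch test can be run from the Table 6 summaries: A, mean -8, SD 7.7, n=37; B, mean -12.2, SD 9.5, n=36.

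- Difference: -8 - (-12.2) = 4.2
- SE = √(7.7²/37 + 9.5²/36) = √(1.602 + 2.507) = 2.027
- t = 4.2/2.027 = 2.07, with about 67 degrees of freedom; two-sided p = 0.042

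Both values lie on the same side of 0.05, so the choice of test does not drive the result.

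**4. Does the rank matter?**

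- *Unadjusted co-primaries, either sufficient:* with two tests at 0.05, the chance of at least one false positive is 1 - 0.95² = 9.75% if they are independent, and at most 2 × 0.05 = 10% under any dependence. At 0.05/2 = 0.025 each, 0.047 fails, as does 0.042.
- *Protocol hierarchy:* IRLS change can be claimed only if the Fisher test on CGI-2 responders is significant. The SAP reports neither that test nor the responder counts. Its only CGI comparison has p=.80, with a mean of 2.1 in both groups.

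**5. Reach of the most-recent-value rule.** The Table 6 footnote lists IRLS follow-up at 1 week (2), 2 weeks (4), 4 weeks (5) and 6 weeks (61). So 2 + 4 + 5 = 11 of the 72 values listed, about 15%, predate week 6. The table's counts do not agree (total 74; groups 37 + 36 = 73; footnote 72), so 11 is a minimum. The Welch result in step 3 includes these values and is not the planned week-6 analysis.

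**The case against.** **The SAP is openly retrospective.** It is in the past tense, speaks of an original plan and contains results, so a careful reader would not take it for a 2014 plan. Title pages are absent from the copy reviewed, so a later version date may stand there. This lowers the risk of misreading, but the header date is still wrong and the departures are still unmarked.

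**IRLS is not new.** A reader might infer that the IRLS comparison itself is post hoc. The documents do not support that. The protocol lists it as the secondary exploratory hypothesis, ranks it second in the hierarchy and names its test. IRLS also appears in the first primary objective and among the primary clinical evaluations. Only the co-primary rank is new.

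**The analysts were masked.** SAP Methods state that investigators and analysts were blind to assignment until the analysis was complete, and a margin comment confirms that group identity was still unknown to its writer. This stands as stated, although the ferritin contrast and the remark in the rationale suggest weak masking. Masked labels do not make a choice prespecified once p-values by group are visible. Equally, the documents do not show when each choice was made, so they do not support an inference that any was picked to obtain significance.

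**The sentence on prespecification concerns numbers.** Later in Methods the added accrual is tied to statistical power, and the excess over plan is disclosed. That is the more natural reading; the sentence need not be a claim that the planned tests were followed. It is still loosely worded, since the planned Fisher test is not reported.

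**The comparison was exploratory anyway.** The protocol calls evaluation of treatment differences a tertiary goal. That is correct, and it makes an unqualified co-primary label harder to justify.

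**Conclusion.** The concern holds for the date and for the status of three choices. The SAP text was written after group-level results under A/B labels were seen. The co-primary rank of IRLS change, the Kruskal-Wallis tests and the most-recent-value rule are not in the protocol and are not marked as departures.

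The consequence lies in rank. As an unadjusted co-primary, IRLS p=0.047 reads as positive, with a family-wise error of 9.75% under independence and up to about 10% otherwise. Under the protocol's order it cannot be claimed unless the responder test is significant, and nothing reported shows that it is. The p=.80 compares scores rather than responder proportions, so it makes a significant Fisher test look unlikely without settling the matter.

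Two further inferences should be avoided. The planned test would not overturn the IRLS p-value on the Table 6 data (0.042 against 0.047). Nor should the error rate be computed over all five p-values in Tables 4 to 6, because neither document defines such a family.

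These conclusions assume that the Table 6 summaries are right, although the analyst's comment says they still need checking, and that no earlier dated record of the SAP's choices exists.

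**What to change.** - Put the true date and version on the SAP, and state that group-level results under A/B labels had been seen when it was written.
- Run and report the protocol analysis first: Fisher exact test on CGI-2 responders at week 6, then Welch's t-test on week-6 IRLS change. Describe IRLS as the prespecified second-step exploratory test, which cannot be claimed unless the first step is significant.
- Label the co-primary status, the Kruskal-Wallis tests and the most-recent-value rule as departures from the protocol, post hoc unless a dated earlier record exists.
- Reword the Summary to say that the 30 patients were added to restore the planned number with outcome data, in place of the statement that the prespecified analysis was maintained.
- Move the text and tables from the Results heading onward into a report. Keep the outcome definitions and the Statistical analysis section in the SAP.

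The cost is one Fisher test and one Welch test on data already held, some rewording, and a less favourable status for the IRLS result.

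### The SAP's statement that everyone stayed blind until the analysis was complete cannot be relied on: its ferritin tables identify Groups A and B while data questions are still open

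*SAP*

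**What the plan says.** **Blinding claim.** SAP, Methods (randomization and blinding paragraph): "All investigators and the Analysts were blind to the assignment until completion of the analysis".

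**Tables by label.** SAP, Results: "The mean change in Ferritin from baseline to follow up was 200.3 and 23.3 for Group A and Group B, respectively". The labels on the ferritin rows of Tables 1 to 3 also head Tables 4 to 6 (global impression, FSS and IRLS) and the adverse-event listings. The SAP's rationale states the expected direction: "IV iron treatment with 1000 mg of IV iron corrects the anemia and provides a better increase in iron parameters".

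**State of the analysis.** The analyst's comments on the Results say "I still need to double check the results" and "I want to confirm that there are no new data to analyze". A further comment says the two labels will be defined once the analyst learns which is which. The Results text also carries the note "NOT SURE IF/HOW YOU WANT TO PRESENT THE ADVERSE REACTION DATA".

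**Protocol rule.** Protocol, Breaking the blind: "The blind for the form of initial treatment will be broken for every cohort of 10 treated patients after all members of a cohort have" finished the study. The trigger is completion of a cohort, not completion of the analysis.

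**Standing of the IRLS test.** The SAP calls IRLS change co-primary with CGI-I. The protocol's tertiary objectives test CGI-2 responders first and IRLS change second. Its Statistical Analyses section names the Fisher exact test and the unequal-variance t-test for these two comparisons.

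**The concern.** A blinding statement tells the reader that choices about records, checks and tests were made without knowing which treatment they would favour. Neutral labels give that protection only if nothing under them reveals the arm. Here a post-treatment marker that differs sharply between IV and oral iron is tabulated under the same labels as the outcomes, before the analysis was finished.

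What is at stake is the one efficacy comparison that reached nominal significance, IRLS change at p=0.047. The questions left open (re-checking, possible new records, inconsistent counts) all concern the records behind it. If they are settled by people who can tell the arms apart and have seen the result, an unqualified claim of blindness gives the reader too much assurance.

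**Working it through.** **1. Do the tables identify the arms?** Inputs from SAP Table 3, change in ferritin:
- Group A, n=34: mean 200.3, SD 133.0, quartiles 103.0 and 290.0.
- Group B, n=33: mean 23.3, SD 21.2, quartiles 9.0 and 27.0, maximum 102.0.

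Ratio of means: 200.3/23.3 = 8.6. Welch t = (200.3 − 23.3)/√(133.0²/34 + 21.2²/33) = 177.0/23.1 = 7.66, p about 6×10⁻⁹. Because 103.0 > 102.0, about three quarters of Group A lie above every Group B patient. With the SAP's own statement that IV iron raises iron parameters more, A is evidently IV and B oral.

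**2. Was the analysis complete when these tables existed?** No. Besides the two open comments, Table 6 does not add up: the total column gives 74, the arms give 37 + 36 = 73, and the follow-up footnote gives 2 + 4 + 5 + 61 = 72. By that footnote, 2 + 4 + 5 = 11 values were taken before week 6. A note under Table 4 tells the analyst to use the latest available value when week 6 is missing.

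**3. Is the printed IRLS p-value plausible?** Kruskal-Wallis needs patient-level data, so 0.047 cannot be reproduced. The protocol's Welch test can be run from Table 6 (A: n=37, −8, SD 7.7; B: n=36, −12.2, SD 9.5):
- SE = √(7.7²/37 + 9.5²/36) = 2.027, df = 67.3.
- t = 4.2/2.027 = 2.07, p = 0.042.
- With inputs rounded to one decimal, p lies between 0.037 and 0.048. If −8 was rounded to a whole number, the range is 0.021 to 0.078.

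The printed value is consistent with the table.

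**4. How close is it to 0.05?**
- The critical difference is 1.996 × 2.027 = 4.05, so the 95% CI is 0.15 to 8.25.
- The margin is 4.2 − 4.046 = 0.154 points on the mean. With SDs held fixed, a change of 0.154 × 36, or about 5.5 points, in one Group B patient brings the Welch p to 0.05. A 10-point change gives 0.057.
- Simulation (assumption: rounded, roughly normal scores matching Table 6, kept when the Kruskal-Wallis p was 0.0465 to 0.0475): deleting one patient took p to 0.05 or above for about 52% of patients, with a range of about 40% to 67% across data sets.
- Adding one Group A patient at −12 did so in about two thirds of data sets or somewhat more (67% to 77% across runs). Adding one at Group A's own mean of −8 did so in about 1%, as did adding one at −12 to Group B.

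**5. Does the protocol agree with the SAP sentence?** No. Cohorts of 10 finish at different times, so a cohort-by-cohort rule opens the early cohorts before any final analysis. The documents do not say whether the rule was followed.

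**The case against.** **The analyst was not unblinded.** A reader might infer that the blinding sentence is false. The documents do not support that: the analyst's comment indicates that the code was not held, and being able to infer the arms differs from being told them or acting on them. No record, test or exclusion is shown to have been chosen by arm. The rationale section has a bracketed author remark regretting that IV iron did not do better. It could simply reflect the null global-impression result, which needs no decoding. This objection stands.

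**The comments are ordinary good practice.** Confirming that the data are complete and verifying output are proper steps, and neither comment describes a decision to add or drop anyone. That is fair. But the questions are open, and the Table 6 counts will require decisions about records.

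**The deletion figure does not measure bias.** Correct. It reflects conditioning on p near 0.047: the share is still 46% with doubled arms and 44% with 100 per arm. It shows closeness to a threshold, no more. Anyone seeing p=0.047 under plain A/B labels would also know which changes matter, so the missing data freeze counts for as much as the decoding.

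**Adverse-event choices.** A reader might infer that the undecided adverse-event presentation could also move the IRLS result. It cannot; it affects only the safety summary.

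**The stakes are limited.** This is a pilot in which the protocol makes treatment comparison a tertiary goal and puts CGI-2 responders ahead of IRLS. The CGI score comparison in Table 4 gave p=0.80; the Fisher test on responders is not shown. If that test is also null, the IRLS p-value has no confirmatory standing under the protocol. This stands, although the SAP's co-primary wording invites a stronger reading.

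**Conclusion.** The blinding sentence cannot be relied on as written. The labels were decodable from the SAP's own ferritin tables, results by label were on the page before data checks were closed, and the protocol's rule for breaking the blind conflicts with the sentence. The supportable description is masking in name, with no evidence that the code was held or that bias occurred.

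The practical exposure is confined to the IRLS comparison: a difference of 4.2 points with a lower confidence limit of 0.15, so one or a few records could change its nominal significance in either analysis. That rests on the printed summaries for the Welch test and on roughly normal scores for the simulation. The comparison is secondary under the protocol's order, so this is a correction to make before reporting, not a reason to set the trial aside.

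**What to change.** 1. Replace the sentence. Say that analysts worked under A/B labels that could be decoded from the iron tables, and that a first analysis was seen before data checks were closed. Reconcile this with the protocol's cohort-by-cohort rule and state when each cohort was actually unblinded.
2. Before the re-check, settle whether there are new data, resolve the 74/73/72 counts and freeze the data set. Document a record-level reason for every addition, exclusion or correction, with group labels and iron results withheld from those deciding.
3. Then run the protocol's tests in its order: Fisher exact for CGI-2 responders, then the unequal-variance t-test for IRLS change. Produce one adverse-event summary whose form was fixed in advance.

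Relabelling the groups with a new scrambled code is not worth doing: the results already seen (−8 against −12.2) would identify the new labels at once. Withholding labels and iron results reduces the exposure but cannot undo the first look, which is why disclosure is needed.

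The cost is a corrected paragraph, a short decision log and a re-run of a few tables. The downside is a weaker blinding claim.
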